6.1.1 Decitabine dosing and schedule

Decitabine is given at a dose of 0.1–0.2 mg/kg/day on days 1, 8, 15, 28 (+/- 3 days)..

All patients will receive at least one dose Decitabine every week. If decided by treating physician that the patient needs a more rapid debulking of high disease burden, a second dose can be added. If Decitabine is given twice a week, should preferably be given on two consecutive days.

6.1.2 Venetoclax dosing and schedule

Venetoclax is dosed at 400 mg by mouth one day a week concurrently with the first decitabine dose (+/- 1 day allowed).. If patients are taking another CYP3A4 inhibitor dose adjustments should be made as recommended by pharmacist for a goal dose of venetoclax of 400 mg.

If patient receives two days of decitabine a week, they still only take venetoclax on the day of the first dose of decitabine (+/- 1 day allowed).

6.1.3 Treatment phase

Each treatment cycle is 28 days. Treatment is given weekly and continued without any interruptions

6.1.4 Dose adjustments for hematologic toxicity

The starting dose of decitabine being administered (0.2 mg/kg) and the dose of venetoclax of 400 mg have been identified by previous pharmacokinetic, pharmacodynamic and clinical studies (administering the drugs singly) as the minimal biologically active doses needed to produce the intended therapeutic molecular pharmacodynamic effect. Based on our experience using this regimen, an anticipated side-effect is neutropenia. However, neutropenia is frequently

caused by the myeloid malignancy being treated. Since doses are already minimal biologically active doses, it is important not to prematurely dose-reduce if neutropenia is from disease and not from therapy:

- To avoid premature dose reduction from already minimal biologically active doses, this protocol incorporates an Induction Phase (week 1-12) during which doses should not be held except for clinically exigent circumstances. After the induction phase, the treating clinical team will need to exercise judgement to distinguish between Grade 4 neutropenia ($ANC < 0.5 \times 10^9/L$) caused by disease *vs* treatment, *aided if necessary with repeat bone marrow aspirate and biopsy*.
- If Grade 4 neutropenia is judged to be from treatment, the first step is to hold treatment until recovery of the ANC to $> 0.5 \times 10^9/L$. If neutropenia recurs, then the next step is to decrease decitabine doses by 25% (0.15 mg/kg).
- If neutropenia recurs even on the reduced dose of decitabine, then decrease dose of decitabine by another 25% (0.1 mg/kg). If neutropenia persists even at this dose and is felt to be from treatment and not from disease, treatment should be held until recovery of the ANC to $> 0.5 \times 10^9/L$. Only continue therapy if it is considered to be in the best interests of the patient. Its at discretion of the treating physician based on clinical benefit to the patient, as to when to go back to the full dose of Decitabine or keep at reduced dose.
- To reduce risks from baseline neutropenia caused by the disease, that may deter or hinder administration of potentially beneficial therapy, this protocol permits concurrent administration of G-CSF (filgrastim or biosimilar $\sim 5 \mu\text{g}/\text{kg}$) if thought to be safe by the treating physician
- Venetoclax can also cause cytopenias but less so with once weekly dosing. If cytopenias are thought to be due to venetoclax, can first decrease dose by 50% (200 mg daily) and if cytopenias persist and is thought to be due to venetoclax, hold venetoclax and continue decitabine single agent. Can restart venetoclax based on the clinical judgment of the treating physician

6.1.5 **Adjustments for non-hematologic toxicity \geq Grade 3**

Low doses of decitabine and weekly venetoclax have low risk of renal toxicity, and are not felt to be renally toxic. There is concern that decitabine has hepatotoxicity at standard dosing, but risk should be nominal in the setting of very low doses. In general, workup for alternative causes for non-hematologic toxicity should be strongly considered, and decitabine and venetoclax is only dose reduced in the absence of alternative explanation. However, doses should be reduced for toxicity considered *at least possibly related* to decitabine and venetoclax. This includes laboratory abnormalities.

Infections in patients with myeloid malignancies are common and should be treated accordingly. Infections do not require dose adjustments unless there is clear evidence of relation to decitabine or venetoclax toxicity leading to the associated infection. In other words, most infections should not warrant dose modification.

Table 1: Adjustments for non-hematologic toxicity

Serum creatinine (Renal Toxicity)	
If pretreatment creatinine is < 0.5, and increased in creatinine to ≥ 1.5
 
If pre-treatment creatinine 0.6-0.8 mg/dL, an increase to ≥ 1.7 mg/dL
 
For pretreatment creatinine of 0.9 to 3.0, and a doubling of creatinine, or > 5.0.
	
If no alternative cause identified and toxicity felt at least possibly related, hold decitabine and venetoclax until recovered below threshold and restarted with a 25% dose reduction. Can go back to full dose when felt safe to do so by treating physician.
 
If toxicity recurs after dose reduction without an identifiable alternate cause and is thought to be related to decitabine or venetoclax, patient should be removed from protocol

-----------------------------------	--	--

Hepatotoxicity	AST or ALT $\geq 3 \times$ ULN OR Direct Bilirubin $\geq 2 \times$ ULN	If no alternative cause and toxicity felt at least possibly related to study drug: Hold until recovery to below threshold and restart decitabine and venetoclax with 25% dose reduction. Can go back to full dose when felt safe to do so by treating physician.
Any other grade 3 and 4 adverse events at least possibly related to decitabine/venetoclax (No adjustments for alopecia)		If no alternative cause suspected or identified : Hold until recovery to grade 1 and restart at 25% dose reduction

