cytopenias. However, MDS and AML are heterogenous diseases and there are many subgroups of patients for whom standard dosing of HMA +/- venetoclax have not been shown to be effective and therefore these patients currently do not have standard of care options available for them. In addition, there are subgroups of patients who are unable to tolerate the toxicities of standard HMA/venetoclax dosing and inevitably receive substandard doses of therapy due to dose delays and interruptions and therefore are unable to receive effective therapies. A non-cytotoxic weekly dosing schedule may be the only effective or practical therapy for these subgroups. Below we give a background on the rationale for each of these subgroups for who we plan to enrol in this study because they currently do not have a standard of care treatment option available to them either because there is no known benefit for their subtype of MDS/AML and/or they are unable to receive currently approved dosing schedules of HMA/venetoclax due to toxicity.

1.3.1 Patients who are unfit and cannot tolerate prolonged cytopenias from standard dosing of Aza/ven:

The standard dosing of Aza/ven used in the VIALE-A trial is Azacitidine 75 mg per square meter of body-surface area subcutaneously or intravenously on days 1 through 7 every 28-day cycle, venetoclax 400 mg orally once daily, in 28-day cycles.¹ A major challenge with “standard dosing” of Aza/ven is severe and prolonged cytopenias,⁸ leading to transfusion dependence, increased risk of bleeding, infections, hospitalizations and poor quality of life. For example, in VIALE-A grade 3 neutropenia was observed in 42% of patients and over 50% required a reduction in the duration of venetoclax. Similarly, in clinical practice clinicians have been struggling with dose limiting cytopenias leading to dose reductions and treatment interruptions. Various algorithms are being suggested how to best dose, and interrupt regimens of Aza/ven, with majority suggesting shorter durations of venetoclax than was used in VIALE-A trial.⁸ It’s therefore not surprising that the real-world experience with standard dosing HMA/ven have reported outcomes to be inferior to the clinical trials.⁹ This has been most challenging for elderly patients with multiple comorbidities and for patients with antecedent bone marrow disorders who have poor hematopoietic reserve, many of whom cannot tolerate standard Aza/ven dosing.

1.3.2 Patients with antecedent Myeloproliferative disorders:

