6.0 TREATMENT PLAN

6.1 Treatment Regimen Overview

Administration: Decitabine is reconstituted with 5 ml sterile water to facilitate subcutaneous administration. Decitabine is given by subcutaneous injection. Venetoclax is taken as a tablet prepared by patients pharmacy.

Venetoclax is given at a dose of 400 mg po once per week concurrently with the Decitabine dose (+/- 1 day allowed).

All treatment regimens may be continued indefinitely.

Concomitant Treatment: Hydroxyurea is permitted to control leukocytosis and thrombocytosis. In patients with aggressive high bulk disease as determined by the investigator and PI, may receive debulking chemotherapy with either Gemtuzumab ozogamicin, Cladribine or Cytarabine prior to starting decitabine/venetoclax. Also patients who have mutations in either FLT3 (ITD or TKD), JAK2, IDH1 or IDH2 mutation may receive concomitant inhibitors (as outlined in the table below) at any point during the protocol as determined by the PI. Other than HU and above mentioned drugs, no other concomitant disease modifying therapy is permitted. No additional investigational study is permitted and concurrent participation in other interventional trials are not permitted. Participation in registry or non-interventional studies is permitted.

Mutation	Medication
FLT3 ITD	Midostaurin Gilteritinib Quizartinib
FLT3 TKD	Midostaurin Gilteritinib
IDH1	Ivosidenib Olutasidenib
IDH2	Enasidenib
JAK2	Jakafi

Induction phase: The initial 12 weeks of therapy is considered an induction phase during which dose modifications or holds are discouraged except for severe toxicity severe, non-hematologic adverse events, as per figure study schema. However, if myelosuppression from medications are suspect, treatment holds and dose modifications may be considered in consultation with the study chairs. Desired treatment holds or dose modifications should be reviewed as soon as possible with the study chairs to determine whether dose hold/modification is acceptable. The purpose of the induction phase is to produce relatively rapid reduction of tumor burden to a level that will permit recovery by more functional hematopoiesis that can relieve cytopenias.

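### The venetoclax reduction step for cytopenia in section 6.1.4 is written as a daily dose, which read literally raises the weekly dose from 400 mg to 1,400 mg

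*Combined protocol and SAP*

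**What the plan says.** The treatment sections agree on the venetoclax regimen. Section 6.1: "Venetoclax is given at a dose of 400 mg po once per week concurrently with the Decitabine dose". Section 6.1.2: "Venetoclax is dosed at 400 mg by mouth one day a week concurrently with the first decitabine dose", and still only one venetoclax day a week when decitabine is given twice. The Study Schema lists venetoclax on days 1, 8, 15 and 22.

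The last bullet of section 6.1.4 covers cytopenias thought to be due to venetoclax. It opens with "Venetoclax can also cause cytopenias but less so with once weekly dosing". Its next sentence says the clinician "can first decrease dose by 50% (200 mg daily) and if cytopenias persist", venetoclax is held and decitabine continues alone. No other current text corrects the frequency.

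On dosing days, the Schema gives day 22 as the fourth day for both drugs, and the Protocol Summary gives day 22 for decitabine. The Protocol Summary gives day 28 for venetoclax (window of 1 day either side), and section 6.1.1 gives day 28 for decitabine (window of 3 days either side).

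**The concern.** The 50% and the 200 mg fit a once-weekly regimen; the word *daily* does not. An instruction meant to halve the dose would, if followed to the letter, increase it, and in a patient whose cytopenia has just been attributed to that drug.

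The error could pass unnoticed. Section 1.3.1 describes the standard schedule as "venetoclax 400 mg orally once daily, in 28-day cycles", and 200 mg daily is exactly half of that, so the order looks familiar. The tablets do not come from a central trial supply: "Venetoclax is taken as a tablet prepared by patients pharmacy".

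Other safeguards are limited:

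- The request that "Desired treatment holds or dose modifications should be reviewed as soon as possible with the study chairs" stands in the induction-phase paragraph of section 6.1. For the later period section 6.1.4 says "After the induction phase, the treating clinical team will need to exercise judgement", in the context of separating disease-related from treatment-related neutropenia. No similar review is written for that period.
- The stopping rule in section 6.5 counts only non-hematologic, non-infectious toxicity in weeks 1 to 12, so worsening cytopenia would not trigger it.
- Section 7.2.2 excludes grade 3 and 4 hematologic laboratory findings from SAEs.
- In the long-term phase the study calendar requires a CBC only at the start of each treatment interval, with more as clinically indicated.

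The day 22/28 conflict is a smaller matter. It leaves two possible dates for the fourth weekly dose.

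**Working it through.** **Inputs.** Full dose: 400 mg, one day a week (sections 6.1 and 6.1.2). Reduction: 50%, written as 200 mg daily (section 6.1.4). Cycle: 28 days, weekly treatment (section 6.1.3). Standard comparison schedule: 400 mg daily (section 1.3.1).

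**The plan's own figure.** Per administration, 0.5 × 400 mg = 200 mg. The amount reproduces. The frequency does not, as the totals show:

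| Reading | Per week | Per 28-day cycle | Ratio to planned |
|---|---|---|---|
| Planned: 400 mg once weekly | 400 × 1 = 400 mg | 400 × 4 = 1,600 mg | 1 |
| As written: 200 mg daily | 200 × 7 = 1,400 mg | 200 × 28 = 5,600 mg | 1,400 / 400 = 3.5 |
| Evident intent: 200 mg once weekly | 200 × 1 = 200 mg | 200 × 4 = 800 mg | 200 / 400 = 0.5 |

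The literal order is 1,400 / 200 = 7 times the intended one.

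**From what dose would 200 mg daily be a 50% decrease?** Only from 400 mg daily: 400 × 7 = 2,800 mg a week, and 1,400 / 2,800 = 50%. That is the standard schedule, not this trial's. The planned regimen is 400 / 2,800 = 14% of it.

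**Dosing days**, with day 1 of the next cycle counted as day 29:

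- Days 1, 8, 15, 22: intervals of 7, 7, 7 and 7 days.
- Days 1, 8, 15, 28: intervals of 7, 7, 13 and 1 days.

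The windows around day 28 are days 27 to 29 (venetoclax) and 25 to 31 (decitabine). Neither reaches day 22, so the windows do not reconcile the two versions. Day 28 also conflicts with the requirement in section 6.1.1 for at least one decitabine dose every week and with the weekly treatment in section 6.1.3.

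**The case against.** The best counter-argument is that no careful reader would escalate the dose. The operative verb is to decrease, the figure is 50%, the sentence before refers to weekly dosing, and every treatment section gives venetoclax once a week. Section 6.1.1 also uses a per-day unit (mg/kg/day) for decitabine, which is not given daily, so *daily* here might mean per dosing day. The step is optional. Section 1.4 (rationale for cohort expansion) reports that none of the first 17 evaluable patients needed a dose reduction, and during induction modifications go to the study chairs.

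Much of this stands: the intent is evident and there is no sign of harm. It does not remove the problem. The decitabine parallel is imperfect, because section 6.1.1 lists the dosing days beside the dose and section 6.1.4 does not. The parenthesis is the only place that states the reduced venetoclax order, and its frequency is wrong. The 17 patients inform only the 12-week induction period; how often the step is used later is unknown. The absence of chair review after induction is inferred from silence rather than stated.

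A further objection is that a fixed 200 mg may not be half of what a patient on a CYP3A4 inhibitor actually takes. Section 6.1.2 adjusts such patients towards a goal dose of 400 mg, so a goal of 200 mg once weekly is still half.

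**Conclusion.** The concern holds. As written, the step in section 6.1.4 turns a stated halving into 3.5 times the planned weekly dose (1,400 mg against 400 mg). It needs correction because it is a safety instruction that contradicts the regimen it modifies.

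The conclusion is limited to milligrams under a literal reading. The documents give no pharmacokinetic data for this step, so nothing is claimed about exposure. Nothing shows that the literal reading has been used, and no effect on the primary-endpoint result is claimed. The day 22/28 conflict is real in the current text but only calls for clarification; the must-fix rating rests on section 6.1.4 alone.

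**What to change.** In section 6.1.4, change the reduced venetoclax dose from 200 mg daily to 200 mg once weekly. This gives 200 mg a week and 800 mg a cycle, the 50% decrease that the text states.

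As a secondary correction, change day 28 to day 22 for venetoclax in the Protocol Summary and for decitabine in section 6.1.1. All dosing intervals are then 7 days, and there is one due date for the fourth dose from which a toxicity-related delay can be counted.

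The cost is a change of frequency wording in one place and one number in each of two places, made by a short clarification or amendment with a memo to sites. Design, sample size and analysis stay as they are.

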6.1.5.1 Identification of differentiation syndrome

The differentiation syndrome is a potentially fatal complication observed in the treatment of acute promyelocytic leukemia with tretinoin, but has also been reported in therapies with epigenetic effects, such as IDH inhibitors.^{19,20} Although rare, there are case reports of differentiation syndrome in patients with HMA therapy.²¹ In general, differentiation syndrome has not been described in other low dose HMA studies, and is *not* an anticipated adverse event. However, with the proposed treatment schedule of decitabine/ven is effective in promoting differentiation of myeloblasts and cytokine release occurs from these cells, this is a potential complication that requires awareness by treating physicians.

The differentiation syndrome is characterized by fever, dyspnea, possible hypoxemia and respiratory distress with pulmonary infiltrates, peripheral edema, hypotension and renal and hepatic insufficiency. If differentiation syndrome is suspected, treatment with corticosteroids should be started promptly. The corticosteroid of choice is Dexamethasone 10mg IV twice daily, which should be continued until resolution of symptoms, signs and laboratory abnormalities related to differentiation syndrome. Hydroxyurea would be permitted in this setting to control leukocytosis.

Decitabine/venetoclax may be continued unless it is a severe case of differentiation syndrome as determined by the treating physician or if there is no improvement after treatment with corticosteroids. If discontinued, decitabine/ven may be resumed without dose adjustment after resolution of differentiation syndrome.

6.2 General Concomitant Medications and Supportive Care Guidelines

Antimicrobial prophylaxis:

Patients with hematologic illnesses should be offered antimicrobial prophylaxis (antiviral, antifungal, antibacterial) per institutional standards.

Supportive care:

G-CSF can be considered for any patient with < 5% bone marrow blasts who has a baseline ANC < 1.5 x 10⁹/L during the induction phase, but should be held if the most recent ANC is \geq 1.5 x 10⁹/L. During the long-term treatment phase, G-

CSF could be administered for neutropenia (ANC < 1 x 10⁹/L), not felt to be due to active disease.

Concomitant erythropoietin analogues are permitted at physician discretion for transfusion dependent patients with EPO level < 500.

Patients with advanced myeloid malignancies often require frequent clinical visits and CBC evaluation for supportive transfusions. Patients should be monitored as per local standards and treating physicians' standard practice. A weekly CBC at minimum during the induction phase of treatment is suggested.

No antiemetic therapy is required per protocol, but any is permitted at treating physician's discretion.

At higher doses, decitabine is known to cause gastrointestinal toxicity, including constipation. Though not anticipated at provided doses, patients should be monitored and treated as indicated for gastrointestinal toxicity.

The need for central venous access can be determined on a case by case basis, per physician discretion, as central lines carry both benefits and risks to patients. However, decitabine should be given subcutaneously in this setting.

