QOL	Quality of life
RARS-T	Refractory anemia with ringed sideroblasts and essential thrombocythosis
R/R	Relapsed refractory
SAE	Severe adverse event
SOC	Standard of Care
ULN	Upper limit of normal
Ven	Venetoclax

[figure not shown]
STUDY SCHEMA

Treatment (28 day cycles):

- Venetoclax 400 mg on day 1, 8, 15, 22 of every cycle
- Decitabine 0.2 mg/kg SQ on days 1, 8, 15, 22 (for aggressive disease will add decitabne on days 2, 9, 16, 23)
- If at baseline or during treatment ANC is $< 1.5 \times 10^9/L$, administer GCS-F (filgrastim or biosimilar) on same day as decitabine if bone marrow blast count is considered to be $< 10\%$. Hold G-CSF if ANC is $> 1.5 \times 10^9/L$

Monitoring:

- CBC and type and screen as clinically indicated
- CBC with differential, CMP, LDH, reticulocyte count every four weeks
- Bone marrow biopsy and aspirate at screening, week 12 and week 24. Additional bone marrow as indicated

PROTOCOL SUMMARY

Protocol Number/Title	Proof-of-concept study of metabolically optimized, non-cytotoxic low-dose weekly decitabine and venetoclax in myeloid malignancies
Study Phase	Proof-of-concept clinical trial
Brief Background	
The combination of Azacitidine and venetoclax is FDA approved for patients AML > 75 and/or unfit for induction chemotherapy. However, majority of patients receiving standard dosing of Aza/Ven require dose interruptions, treatment delays and dose reductions. In addition, Aza/ven has limited activity in various subgroups of myeloid malignancies such as P53 mutant MDS/AML.
 
The severe cytopenias encountered with Aza/ven is particularly challenging for patients with poor hematopoietic bone marrow reserve such as MDS and MF. Also some elderly patients with comorbidities cannot tolerate the prolonged cytopenias caused by Aza/ven. This pilot clinical trial will evaluate the tolerability of a non-cytotoxic regimen for patients with myeloid malignancies who either cannot tolerate or are not known to benefit from standard Aza/ven dosing.

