2.2 Secondary Objective(s)

1. Percentage of MDS participants with complete remission (CR) and complete remission with incomplete marrow recovery (CRi)
2. Percentage of AML participants with complete remission (CR) and complete remission with incomplete marrow recovery (CRi)
- 3.

This will be calculated based on current International Working Group (IWG) criteria. CR is defined as absolute neutrophil count $> 1000/\text{microliter (mCL)}$, platelets $> 100k/\text{mCL}$, red cell transfusion independence, and bone marrow with $< 5\%$ blasts. CRi is defined as bone marrow with less than 5% blasts, and absolute neutrophils of $\leq 10000/\text{mCL}$ or platelets $\leq 100k/\text{mCL}$

4. Event-free survival (EFS)

EFS will be defined as the number of days from randomization to the date of progressive disease, relapse from CR or CRi, treatment failure or death from any cause.

5. Complete remission or complete remission with partial hematologic recovery rate (CR+CRh)

A response of CRh is defined as Bone marrow with $< 5\%$ blasts, peripheral blood neutrophil count $> 0.5 * 10^3/\text{mCL}$ and peripheral blood platelet count $> 0.5 * 10^5/\text{mCL}$.

6. Post baseline transfusion independence rate

Transfusion Independence is defined as a period of 56 days with no transfusion between first dose of study drug and the last dose of study drug + 30 days. The rate of conversion for red blood cells (RBC) and platelets is defined as percentage of participants being post-baseline transfusion independent from baseline transfusion dependence.

7. Rate of Hospitalization

Defined as hospitalization for complication related to myeloid malignancy or treatment. Initial admission for diagnosis or initiation of therapy will not be considered an event.

8. Infection rate requiring hospitalization

Defined as being hospitalized due to an infection or sepsis.

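### The Study Schema, Section 6.1.4 and Section 6.2 give conflicting instructions on who receives G-CSF, and when, and need to be reconciled

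*Combined protocol and SAP*

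**What the plan says.** G-CSF is addressed in three places, all current text.

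- **Study Schema, treatment list.** The condition opens "If at baseline or during treatment ANC is" below 1.5 x 10^9/L. The instruction is to "administer GCS-F (filgrastim or biosimilar) on same day as decitabine if bone marrow blast count is considered to be" below 10%. G-CSF is held when ANC is above 1.5.
- **Section 6.2, supportive care.** In the induction phase, "G-CSF can be considered for any patient with < 5% bone marrow blasts" and a baseline ANC below 1.5, with a hold once the latest ANC is 1.5 or higher. In the long-term phase it may be given for ANC below 1 x 10^9/L if active disease is not thought to be the cause. That second sentence carries no blast limit.
- **Section 6.1.4, hematologic dose adjustments.** To reduce the risk from disease-related baseline neutropenia, "this protocol permits concurrent administration of G-CSF" when the treating physician thinks it safe. No blast or ANC limit is given.

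None of these cross-refers to another as controlling. Footnote 7 of the Section 10.0 calendar, on the study-treatment row, sends staff to both the schema and Section 6. Section 5.0 names three recruiting centers.

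**The concern.** Staff who follow the schema and staff who follow Section 6.2 can reach different decisions for the same patient while each complies with the protocol. That is first a patient-safety matter, because it concerns a growth factor given to neutropenic patients with residual marrow blasts.

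It may also matter for the data. G-CSF raises the neutrophil count, and several outcomes use ANC cut-offs: CR against CRi and CRh in Section 2.2, CR in Tables 3 and 5, and neutrophil improvement in Table 2. No rule was found for counts measured under G-CSF; the Table 2 footnote on pretreatment values deals only with transfusion. Uneven G-CSF use could add variation to these outcomes that would be hard to recognize afterwards.

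**Working it through.** No sample size, alpha or power figure depends on this point, so the main check is a side-by-side reading. ANC is in 10^9/L.

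| | Schema | 6.2, induction | 6.2, long-term | 6.1.4 |
|---|---|---|---|---|
| Force | directive | optional | optional | permitted if judged safe |
| ANC trigger | < 1.5 | < 1.5 | < 1 | none stated |
| Which ANC | baseline or during treatment | baseline | in that phase | baseline neutropenia from disease |
| Marrow blasts | < 10% | < 5% | no limit; not due to active disease | no limit |
| Hold | ANC > 1.5 | latest ANC >= 1.5 | none stated | none stated |

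**Where the schema and Section 6.2 diverge**

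1. Induction, blasts 5% to below 10%, ANC below 1.5: the schema directs G-CSF; the patient is outside the Section 6.2 criterion.
2. Induction, blasts below 5%, baseline ANC below 1.5: directed by the schema, optional in Section 6.2.
3. Induction, baseline ANC 1.5 or higher that later falls below 1.5, blasts below 10%: covered by the schema, not by Section 6.2.
4. Long-term phase, ANC 1.0 to below 1.5, blasts below 10%: directed by the schema, not covered by Section 6.2.

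**How this could reach the ANC-based responses**

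CR and CRi both require marrow blasts below 5% (Section 2.2 and Table 5; Table 3 allows exactly 5% for CR in MDS). A patient being sorted between them therefore already meets both blast limits, apart from that boundary. The 5% against 10% conflict can act only earlier, while an older marrow result guides treatment. The schema schedules marrows at screening, week 12 and week 24, with extra ones as indicated, so a screening result may guide much of induction. At the time of response, what still differs is directive against optional use, and baseline ANC against any ANC.

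**Sensitivity of the CR rate (illustration only)**

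Inputs from Section 13.0: 32 MDS patients with an expected CR rate of 36%; 38 AML patients with 38%. The standard error is sqrt(p(1-p)/n).

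- MDS: sqrt(0.36 x 0.64 / 32) = 8.5% (plan: no greater than 9%).
- AML: sqrt(0.38 x 0.62 / 38) = 7.9% (plan: no greater than 8%).
- One patient moved between CR and CRi shifts the CR rate by 1/32 = 3.1 points in MDS, or 1/38 = 2.6 points in AML.
- Three patients shift it by 3/32 = 9.4 points or 3/38 = 7.9 points, about one standard error.

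These figures show what each reclassified patient would be worth. The documents give no basis for how many there would be. A combined CR plus CRi rate would be largely unaffected, since CRi accepts a low ANC.

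**Recording**

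The Section 10.0 calendar marks concomitant medications at screening and induction. As the table reads, the long-term and end-of-treatment columns are blank, although marrow response continues to be assessed every three months in the long-term phase.

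**The case against.** The best defense is that the texts can largely be read together. Section 6.2 is permissive and does not forbid G-CSF at 5% to 10% blasts. Section 6.1.4 is a general permission that can be taken as deferring to the detailed criteria. Physician judgement runs through all of this. The trial has one arm and no site comparison, and the schema lists G-CSF as part of treatment. Even a reconciled rule would leave some variation between sites if use stays optional.

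Much of this stands. It shows that the passages do not give opposite commands and that the direct clash is between the schema and Section 6.2. It does not remove the clash: a directive with one set of criteria and an option with another, narrower set are different instructions, and nothing ranks them.

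Three stronger readings are tempting, and the documents do not support them.

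- *That the conflict drives the primary endpoint through Grade 4 neutropenia holds.* Section 6.1.4 places that hold rule after induction, whereas the Protocol Summary and Section 13.0 measure the endpoint in weeks 1 to 12. The only route is the discretionary hold for suspected myelosuppression in Section 6.1, which is discouraged and needs consultation with the study chairs. The cohort-expansion rationale in Section 1.4 reports one interruption among 17 evaluable patients.
- *That the 5% to 10% blast band in Table 3 shows many MDS patients are affected.* That band is a stratum for defining progression. It says nothing about how many of the 32 fall within it.
- *That site differences would show up as regimen effects.* This is conjecture, with no figure in the documents behind it.

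**Conclusion.** The contradiction holds and lies in operative text. The schema and Section 6.2 differ on blast limit, ANC trigger, which ANC counts, phase, and whether G-CSF is directed or optional; Section 6.1.4 adds a permission without thresholds. At least four kinds of patient receive different instructions depending on the page consulted. The wording conflict is certain.

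The number of patients affected cannot be derived. Any effect on CR against CRi, CRh or neutrophil improvement, or on discretionary induction holds, is possible but unquantified, and for CR against CRi the blast-limit part of the conflict acts only indirectly. The correction should be made on grounds of safety and consistent conduct. It does not call the design or the sample size into question.

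The recording gap rests on reading the blank calendar cells as intended; they could be a table-extraction fault.

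**What to change.** Reconcile the Study Schema, Section 6.1.4 and Section 6.2 into one statement, placed once and cross-referenced from the other two places. It should settle the marrow-blast criterion, the ANC trigger and hold boundary, whether baseline or current ANC counts, the treatment phase, and whether use is required or optional. The clinical content is for the sponsor to decide; this review endorses no threshold.

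Extend concomitant-medication recording in the Section 10.0 calendar to the long-term phase, with G-CSF start and stop dates, so that ANC-based responses can be read against G-CSF use.

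The cost is a wording amendment in three places and one added calendar entry. No change to sample size or analysis method is needed.
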